4 SELECTION AND ENROLLMENT OF PARTICIPANTS

4.1 Inclusion Criteria

To be eligible to participate, an individual must meet all of the following criteria:

1. One adult parent/legal guardian has provided signed and dated informed consent form agreeing to the child's participation and the parent's own participation. If a parent/legal guardian is providing consent for a child's participation and a different adult caregiver will be participating, the other adult caregiver must consent to their own participation
 - a. A parent/legal guardian must be willing to also be enrolled in the study and be legally able to consent to their own participation in the research (18 years or over). Parents/legal guardians who are under 18 years and remain in the care of their parents are likely to have a different level of caregiving and support than those who are adults which may impact the delivery of the intervention and assessment visits. If one parent is over 18 years, that parent can participate.
 - b. Inclusion criteria for the adult is that they will be a caregiver for the enrolled infant
 - c. Stated willingness to comply with all study procedures and availability for the duration of the study
2. Infants with HIE based on the modified Sarnat Exam on admission¹⁷ and has started to receive therapeutic hypothermia for 72 hours.¹⁸ Or infants with neonatal encephalopathy.
3. Cared for in the Newborn and Infant Critical Care Unit (NICCU) at Children's Hospital Los Angeles (CHLA) or by referral from other local NICUs.
4. Family lives within 60 miles of CHLA.

4.2 Exclusion Criteria

An individual who meets any of the following criteria will be excluded from participation in this study:

1. Infant born preterm.
2. Infant with congenital anomalies, chromosomal or microarray abnormalities.
3. Infant with microcephaly.
4. Infants who have been redirected for comfort care.
5. Infants who are medically unstable.

4.3 Study Enrollment Procedures

- The medical records of all infants with HIE or NE at the CHLA NICCU will be screened for eligibility, i.e. searching for infants who had a diagnostic/ICD-10 code associated with HIE, including neonatal encephalopathy, birth depression, intrapartum asphyxia.
- Parents of eligible infants will be taken to a private space, provided information about the study, and asked to consent to the study. Documentation of reasons for ineligibility and for non-participation of eligible candidates will be completed using a screening log in REDCap.
- Once consented, infants will receive standard care plus sensorimotor intervention (SMI). If referred by other local NICU, infants will follow the same procedure of consenting within 72 hours of discharge.

4.4 Withdrawal Criteria

- Participants are free to withdraw from participation in the study at any time upon request. The reason for participant discontinuation or withdrawal from the study will be recorded in the participant tracking records in REDCap. Participants who sign the informed consent form, and receive the study intervention, and subsequently withdraw, or are withdrawn or discontinued from the study, will not be replaced.
- Significant study intervention non-adherence (Losing touch with the family / missing more than 5 visits without contacting the research team.)
- Infants who become medically unstable prohibiting participation in more than 1 assessment or 3 days of intervention will be dropped from the study.
- If any clinical adverse event (AE), or other medical condition (i.e. Acute Fractures, Cancer, etc) or situation occurs such that continued participation in the study would not be in the best interest of the participant or they will be unable to participate fully.
- Participant unable to be reached.

5 **STUDY INTERVENTIONS**

5.1 **Interventions, Administration, and Duration**

Standard care intervention provided to infants. Intervention will begin after an infant has met the following conditions: extubated and weaned to respiratory support that is ≤ 2 L per minute canula flow, not requiring vasopressors, and no diagnosis of status epilepticus for ≥ 24 hours. Infants will receive standard care in their respective NICCU and community. Typical service in the NICCU will include routine medical care, physical, occupational, or speech therapy assessments and referral to the infant's local Early Intervention program as deemed necessary by the medical team. All infants will be referred to the High-Risk Newborn Follow-Up Clinic per current clinical policy.

SMI intervention. Infants will receive 2 SMI intervention sessions in the CHLA NICCU (omitted if infant referred from other NICU) and 8 SMI intervention sessions in the home, at CHLA or at the USC Health Science Campus (parent choice) at 1, 3, 5, 8, 11, 15, 20, 26 weeks post NICCU discharge. They can also occur via telehealth. These intervention sessions will be provided by licensed occupational and physical therapists and are considered best practice therapeutic interventions. The 2 intervention sessions in the NICCU will consist of collaborating with parents to recognize their infant's cues to engage in interaction, readiness for sensory exposures, and anticipatory guidance on the transition to home.¹⁰ The 8 intervention sessions in the home will focus on supporting the parents to read their infant's cues to identify the ideal times for interaction and provide 20 minutes of daily intervention addressing four key principles:^{12,16} encourage 1) self-initiated movement, 2) movement variability, 3) visual and manual object interaction, and 4) social interaction. Parents are encouraged not to impose movement on the infant but to encourage movement through environmental enrichment. If the infant is at CHLA at 2 weeks after therapeutic hypothermia, the sessions can be done at CHLA or via telehealth until the child is discharged home.

Education and interventions in the NICCU setting will be supported by standard written parent education materials and access to videos via a website. Refer to NICCU SMI Parent Activities. The aim of education centers around connecting parents to their infants, helping them understand how to read and respond to their infant's cues, identifying the important influence of the sensory environment, and to drive parents to engage in specific amounts of positive, evidence-based, developmentally appropriate sensory exposures each day. Log sheets are provided to track the sensory experiences that parents do with their infants. The higher frequency of visits shortly after NICCU discharge are designed to support parent's questions and the rapid developmental changes seen in this period. A website is available to provide video-based examples of play activities to parents. Handouts with anticipatory guidance on general wellness information such as sleep strategies, calming, and parent self-care will also be provided at these early visits. The intervention supports sensorimotor development and parent engagement and increased opportunities for motor and cognitive based play and interaction.

Parents will be provided with a SPEEDI Home Activity Guide and Log including multiple stages of difficulty for each activity to encourage progression of the activities and access to a website with video examples of each activity. Refer to Home SMI Parent Activities. Parent are encouraged to gradually advance the stages of difficulty for the activities to provide their infant with the “Just Right Challenge.” While specific activities are provided, they are designed to support use of the principles in daily play sessions and to encourage parents to think creatively about how they can expand the infant’s experiences while supporting their learning. We plan for a therapist and parent to meet every 2-6 weeks in person to collaborate to re-assess the infant’s new skills and determine which stage or duration of each activity is the “Just Right Challenge” for the infant.

Fidelity of the therapist and parent delivered intervention has been assessed in our preliminary work to be excellent,^{15,16,19} and we will use the same fidelity measures in the proposed study.

5.2 Handling of Study Interventions

Refer to NICCU SMI Parent Activities for details of NICUU intervention.

Refer to Home SMI Parent Activities for details of home, CHLA or USC intervention.

5.3 Concomitant Interventions

The alternative to participation is not to participate. No participant is asked to change their standard medical and therapeutic care. So, there is not an alternative treatment option.

5.4 Adherence Assessment

Parent-infant dyads who participate in less than 70 percent of the planned intervention sessions will be considered as not being adherent.

6 STUDY PROCEDURES

6.1 Schedule of Assessments

Assessment	Screening	Baseline, Enrollment, Randomization: (Baseline survey)	NICCU Intervention (2 sessions)	NICCU Discharge Assessment (A1)	Home Intervention (6 sessions)	3-month Assessment (A2)	Home Intervention (2 sessions)	6-month Assessment (A3)
Informed Consent Form	X							
Inclusion/Exclusion Criteria	X							
Medical History (medical reports)	X	X		X		X		X
Enrollment/Randomization		X						
Maternal Confidence Questionnaire		X		X		X		X
Analysis of Neuroimaging Data				X				
Test of Infant Motor Performance				X		X		
Bayley-4								X
General Movement Assessment				X		X		
Hammersmith Infant Neurological Examination						X		X
Activity log (weekly)			X	X	X	X	X	X
AHEMD-IS Inventory				X		X		X
Demographics				X				
Parent Stress Index-Short Form				X		X		X
Rehabilitation Services Questionnaire				X		X		X
Sensory Profile 2				X		X		X
Adverse events		X	X	X	X	X	X	X

6.2 Description of Evaluations

6.2.1 Screening Evaluation

Screening

The medical records of all infants with HIE admitted to the CHLA NICCU will be screened for eligibility by study staff. Parents/legal guardians of eligible infants will be provided with a recruitment flyer by NICCU staff or the study team that is also NICCU staff. The study will be explained to the parent/legal guardians and they will have an opportunity to consider their interest in learning more.

Consenting Procedure

If the parent/legal guardian wishes to hear more about the study a study team member who has completed the NIH GCP training and has been trained to obtain consent without coercion will meet with the parent in the NICCU or a quiet meeting area to review the consent form. Parents will be provided an opportunity to ask any questions and as much time as needed to review the consent and discuss it with family and friends. Once all the parent/legal guardian questions are answered they will be asked to sign the consent if they would like to consent to their infant and themselves participating in the study. Only one parent will be required to sign the consent form, however space will be provided for 2 parents to sign the consent agreeing to their own participation as in the past in some instances both parents have expressed interest in participating. Although we will target the parent who will be home with the infant most after NICCU discharge to fully participate in the study, if both parents sign the consent they can both participate in the intervention and assessment visits.

The consent process can be done in person, via phone or via teleconferencing. Parents who choose to participate will sign the consent using REDCap. REDCap will be used to store the consent form. Documentation of reasons for ineligibility and for non-participation of eligible candidates will be completed using a screening log in REDCap.

6.2.2 Enrollment, Baseline, and/or Randomization

Enrollment

Enrollment is defined as the date that the parent/legal guardian agrees to participate and signs the consent form.

- Once consented, infants will be assigned to standard care plus sensorimotor intervention (SMI). If referred by other local NICU, infants will follow the same procedure of consenting and randomization within 72 hours of discharge.

General Assessment Information

All infants enrolled in the study will participate in the same assessment schedule. An assessor blinded to previous assessments will conduct all assessments. Inter-rater reliability on 10% of the visit will be assessed through scoring of videotaped

assessments. Given the high risk of cerebral palsy in this population, outcome measures described as “Highly Recommended” by the NINDS Common Data Elements for Cerebral Palsy were used for each domain.

The assessors will not discuss intervention with the interventionist. Some assessments will be videotaped and scored via video by coders.

For standardized assessments completed in the CHLA NICCU (Test of Infant Motor Performance, General Movement Assessment), they will be completed by a trained, licensed occupational or physical therapist with privileges in the CHLA NICCU and experience handling infants who are medically fragile.

If parents request information from the standardized assessments, the scores of the Test of Infant Motor Performance and Bayley Scales of Infant and Toddler Development can be provided. The PI will share the information with the participant via phone.

Description of All Assessments (alphabetical order)

Activity log. Parents will be asked to complete a log of their child’s activities across one day per week, randomly selected, for the 26 weeks from baseline to the end of intervention. Parents who have a smartphone will be offered a free, custom designed smartphone app and will be sent an alert to complete the log reflecting activity in the last 12 hours.²⁰ Parents without a smartphone or who prefer email will be sent an email to a REDCap survey to complete the log.

Affordances in the Home Environment for Motor Development Infant Scale (AHEMD-IS) Inventory: AHEMD is a standardized questionnaire used to quantify access to types of toys or environments in the home. Parents complete this questionnaire at NICCU discharge, and when the infant is 3 months and 6 months of age, via REDCap.

Bayley Scales of Infant and Toddler Development, 4th edition (Bayley-4). The Bayley-4 is a therapist-administered, primary outcome measure. The Bayley-4 is a valid and reliable norm-referenced test designed to assess multiple developmental domains including cognition and motor abilities of infants between 1 to 42 months.²¹ The Bayley-4 test-retest reliability is provided within each age bracket for each subtest domain (.67-.94), and test content demonstrated good validity. The Bayley-4 will be completed at 6 months of age.

Demographics: Parents will complete demographic and social history using forms F2197_Demographics and F2198_Social Status from the CDE using REDCap at NICCU discharge.

General Movement Assessment (GMA). The GMA is a therapist-administered measure for the early detection of cerebral palsy to characterize the participants. The

GMA was developed to distinguish between infants with and without motor dysfunction and predict which infants may have future motor delays.^{22,23} All infants will be assessed using the GMA at NICCU discharge and at 3 months of age.²² At NICCU discharge, the GMA will be scored by a certified assessor as general movements that are: normal, poor repertoire, cramped-synchronous, chaotic, or hypokinesia. Cramped-synchronous movements are highly predictive of cerebral palsy. At 3 months of age, the GMA will be scored by a certified assessor as normal fidgety, abnormal fidgety, or absent fidgety. Absent fidgety movements are highly predictive of cerebral palsy.

Hammersmith Infant Neurological Exam (HINE). This is a therapist-administered measure for the early detection of cerebral palsy to characterize the participants. The HINE is a standardized and scoreable neurological exam used as part of a comprehensive clinical profile to diagnose cerebral palsy.^{24,25} The HINE will be assessed at 3 and 6 months. Infants who score less than 57 at 3 months or 63 at 6 months will be considered as having an abnormal HINE score.

Maternal Confidence Questionnaire (MCQ). The MCQ consists of 14 questions, and aims to assess maternal confidence in parenting. It has fair test-retest reliability (0.69) and good internal consistency with Cronbach's alpha between 0.86 to 0.93. Parents complete this questionnaire at baseline, NICCU discharge, and when the infant is 3 months and 6 months of age, via REDCap.

Medical Record Review / Medical Updates. A combination of medical records and parent interview will be used to describe the medical history of enrolled participants using the F2203_Medical History and F2207_Surgical and Hospitalization History. While infants are in the NICCU the medical record will be used exclusively (baseline and NICCU discharge assessments). After NICCU discharge parents will be asked to complete these forms via REDCap when the infant is 3 and 6 months of age. Parents will be asked for HIPAA authorization for the research team to attain the following medical records to describe the participants: NICCU discharge summary and neurology, neuroimaging and High-Risk Infant Clinic reports through 2 years of age.

Neuroimaging Data Collected as Part of Routine Clinical Care. Neonates will undergo magnetic resonance imaging (MRI) using a standardized MRI protocol, which was developed for use across sites and MRI platforms as part of the NIH-funded phase III High-dose Erythropoietin for Asphyxia and Encephalopathy (HEAL) Trial. This protocol includes: structural T1- and T2-weighted MRI scans, Diffusion Tensor Imaging (DTI) and MR Spectroscopy. Data from the participants will be processed offline by a single investigator ([name]) who is masked to the infant's history and clinical course. The locus and degree of brain injury will be scored using the Washington University HEAL scoring system. Additionally, regions of interest (ROIs) will be placed in the ventrolateral thalami, posterior putamen and corticospinal tract at the level of the midbrain (cerebral peduncles), posterior limb of the internal capsule and corona radiata and used to extract fractional anisotropy (FA), axial (AD) and radial diffusivity (RD). Together these data will be used to

characterize the degree of HIE brain injury and involvement of the corticospinal tract and deep gray nuclei (thalami, putamen). These variables will be tested as potential moderators of treatment effects in future studies.

Parent Stress Index- Short Form: This measure will be completed via REDCap to consider if the intervention adds stress to families lives. While not directly related to the aims of the study this measure is important to making future clinical recommendations. The Parenting Stress Index—Short Form was used as a self-report instrument to measure level of stress directly associated with the parenting role. The PSI-SF measures stress directly associated with the parenting role. The PSI-SF consists of 36 statements, and parents respond to each statement using a 5-point scale to indicate the degree to which that item has been disturbing to them in the past week. This instrument yields scores for several factors in addition to a Total Stress score. The Total Stress score, utilized is a composite score of the subscale scores. Parents who obtain a Total Stress score above a raw score of 90 are considered to be experiencing clinically significant parenting stress. Internal consistency reliability for the composite Total Stress is reported by the author to be .91. Stability of the instrument was assessed by test-retest after a 6-month interval and yielded an alpha of .84 for the Total Stress. The PSI-SF has recently been validated by independent research efforts. Parents complete this questionnaire at NICCU discharge, and when the infant is 3 months and 6 months of age, via REDCap.

Rehabilitation Services Questionnaire: The F2201 Rehabilitation Therapies Episodes Care form CP version 1.0 will be used to collect the CDE related to rehabilitation services including Early Intervention services via REDCap. This form will be completed at all visits. The total number of non-study related sessions of Physical Therapy, Occupational Therapy, and Speech Therapy services in either the NICCU, Early Intervention or and outpatient setting will be calculated for the time between each assessment visit.

Sensory Profile 2. The Sensory Profile 2 (short form) is a questionnaire of the infant's sensory system.²⁶ It is used in clinical practice and research and has good test-retest reliability ($\alpha=0.81-0.90$), validity, and internal consistency ($\alpha=0.83$). Summary scores for Tactile Sensitivity, Taste/Smell Sensitivity, Movement Sensitivity, Auditory Filtering, Under Responsiveness/Seeks Sensation, Low Energy/Weak, and Visual/Auditory Sensitivity were used as outcomes. Parents complete this questionnaire at NICCU discharge, and when the infant is 3 months and 6 months of age, via REDCap.

Test of Infant Motor Performance (TIMP). The TIMP is a therapist-administered, primary outcome measure. The TIMP is a standardized test for assessing neuromotor development of infants between 34 weeks post menstrual age and 4 months.^{27,28} The TIMP is reliable and sensitive to changes in motor performance with increasing age and skill. The TIMP has been used in clinical trials and is considered to be an excellent discriminative, evaluative, or predictive instrument for at risk infants. The TIMP will be completed at NICCU discharge and at 3 months of age.

Baseline survey: Baseline survey in the CHLA NICCU as soon as infants are enrolled in the study and before they start intervention.

1. Medical Record Review by the study team
2. Maternal Confidence Questionnaire by parents, entered directly into REDCap.

6.2.3 Assessments

Assessment #1: Before NICCU discharge or within the first week after NICCU discharge but before starting intervention in the home, at CHLA, or at USC.

1. Medical Record Review by the study team
2. Test of Infant Motor Performance
3. General Movement Assessment
4. Neuroimaging data collected as part of routine clinical care
5. Parent surveys, entered directly into REDCap
 - a. Affordances in the Home Environment for Motor Development Infant Scale (AHEMD-IS) Inventory
 - b. Demographics
 - c. Maternal Confidence Questionnaire
 - d. Parent Stress Index- Short Form
 - e. Rehabilitation Services Questionnaire
 - f. Sensory Profile 2
6. Collect Activity log from parents
7. Adverse events. Refer to section 7.3 for further details.

Assessment #2: at 3 months of age.

1. Medical Record Update by parents
2. Test of Infant Motor Performance
3. General Movement Assessment
4. Parent surveys, entered directly into REDCap
 - a. Affordances in the Home Environment for Motor Development Infant Scale (AHEMD-IS) Inventory
 - b. Maternal Confidence Questionnaire
 - c. Parent Stress Index- Short Form
 - d. Rehabilitation Services Questionnaire
 - e. Sensory Profile 2
5. Collect Activity log from parents
6. Adverse events. Refer to section 7.3 for further details.

6.2.4 Final Assessment and Criteria for discontinuing study intervention.

Final Assessment: Assessment #3 at 6 months of age

1. Medical Record Update by parents
2. Bayley Scales of Infant and Toddler Development, Edition 4
3. Parent surveys, entered directly into REDCap
 - a. Affordances in the Home Environment for Motor Development

- Infant Scale (AHEND-IS) Inventory
- b. Maternal Confidence Questionnaire
- c. Parent Stress Index- Short Form
- d. Rehabilitation Services Questionnaire
- e. Sensory Profile 2
- 4. Collect Activity log from parents
- 5. Adverse events. Refer to section 7.3 for further details.

Criteria for discontinuing study intervention.

1. Participants will discontinue intervention if the parents report a change in medical status that makes the child ineligible based on exclusion criteria.
2. Intervention will be discontinued if participants experience moderate or worse adverse events which results in a change in availability to complete the intervention
3. A participant may always be removed from intervention whenever the participants' family wishes and alerts the PI.

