1 STUDY OBJECTIVES

1.1 Primary Objective

Primary Objective: Feasibility Aims

1. Is it feasible to complete 1 baseline survey, 1 assessment and 2 parent/therapist collaborative SMI intervention sessions with infants with moderate or severe HIE or NE prior to NICCU discharge?
H1: $\geq 80\%$ of eligible infants will enroll and complete 1 baseline survey, 1 assessment and 2 intervention visits.
2. What proportion of parents complete $\geq 80\%$ of the recommended SMI intervention?
H2a: Parent/infant dyads will complete at least 8 of 10 recommended visits with the therapist.
H2b: Parents will report daily completion of interventions on 80% of randomly sampled days.
3. What proportion of parents complete 100% of the baseline and 3 assessment visits?
H3a: Parent/infant dyads will complete the baseline and 3 assessment visits.

Secondary Objectives

4. Is it feasible to evaluate the impact of brain lesion location on response to intervention?
H4: $\geq 50\%$ of enrolled infants will have an MRI with tractography and cortical volume measurement post therapeutic hypothermia.

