9 STATISTICAL CONSIDERATIONS

9.1 General Design Issues

This is a clinical trial (CT) to evaluate the feasibility and begin to evaluate the effect of early sensorimotor intervention (SMI) for infants with HIE.

Primary Endpoint:

- Assessment 3 when the infants are 6 months of age and infants have completed the intervention

Secondary Endpoints:

- Assessment 1 at NICCU discharge when infants have completed the NICCU intervention
- Assessment 2 when the infants are 3 months of age and have completed part of the intervention.

Refer to Study Objectives on page 3 for primary and secondary hypothesis.

Refer to Outcome Measures on pages 12-14 for alphabetical list of outcome measures with validity and reliability data.

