9.5 Data Analyses

Descriptive statistics will be used to describe the study sample. All outcome measures will be reviewed for outliers and assessed for normality.

Given the small sample size, means and standard deviations (SD), frequency and proportions will be compared without statistical analysis depending on assessments of normality. Bayley-4 motor and cognitive composites will be quantified at 6 months for use in future clinical trial planning.

Primary Objective: Feasibility Aims

1. Is it feasible to complete 1 baseline survey, 1 assessment and 2 parent/therapist collaborative SMI intervention sessions with infants with moderate or severe HIE prior to NICCU discharge?
H1: $\geq 80\%$ of eligible infants will enroll and complete 1 baseline survey, 1 assessment and 2 intervention visits. - This will be assessed using frequency and proportions.

2. What proportion of parents complete $\geq 80\%$ of the recommended SMI intervention?
H2a: Parent/infant dyads will complete at least 8 of 10 recommended visits with the therapist. - This will be assessed using frequency and proportions.
H2b: Parents will report daily completion of interventions on 80% of randomly sampled days. - This will be assessed using frequency and proportions.
3. What proportion of parents complete 100% of the baseline and 3 assessment visits?
H3a: Parent/infant dyads will complete the baseline and 3 assessment visits.

Secondary Objectives:

4. Is it feasible to evaluate the impact of brain lesion location on response to intervention?
H4: $\geq 50\%$ of enrolled infants will have an MRI with tractography and cortical volume measurement post therapeutic hypothermia. - This will be assessed using frequency and proportions.

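### H1 has no time limit and Assessment 1 may follow discharge, so the assessment part of Aim 1 can be met without showing feasibility before NICCU discharge

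*Combined protocol and SAP*

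**What the plan says.** **The question.** Section 1.1 asks, as the first primary aim, whether one baseline survey, one assessment and two SMI sessions can be completed "with infants with moderate or severe HIE or NE prior to NICCU discharge". Section 9.5 repeats the question as "with infants with moderate or severe HIE prior to NICCU discharge", without NE.

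**The criterion.** H1 reads the same in both sections: at least 80% "of eligible infants will enroll and complete 1 baseline survey, 1 assessment and 2 intervention visits". It gives no date, place or reference to discharge. Section 9.5 adds only that frequencies and proportions will be used.

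**The timing of Assessment 1.** Section 6.2.3 allows it "Before NICCU discharge or within the first week after NICCU discharge but before starting intervention in the home". Section 9.1 describes it differently: "Assessment 1 at NICCU discharge when infants have completed the NICCU intervention".

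**The other H1 items.** Section 6.2.2 places the baseline survey in the CHLA NICCU, before intervention starts. Section 5.1 places the two early SMI sessions in the CHLA NICCU and omits them for infants referred from elsewhere.

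**Planned reporting of timing.** The Précis (Design and Outcomes) says that timing will be reported for the SMI sessions under Aims 1 and 2. It makes no such statement for Assessment 1.

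**Population wording.** Section 6.2.1 says "The medical records of all infants with HIE admitted to the CHLA NICCU will be screened for eligibility by study staff", whereas section 4.3 screens for both HIE and NE. Inclusion criterion 2 (section 4.1) admits infants with NE and states no severity grade, although Aim 1 speaks of moderate or severe disease.

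**The concern.** The question and its success criterion do not match. An Assessment 1 done, say, six days after discharge is compliant under section 6.2.3 and counts as a completed assessment under H1, but it is a failure of what Aim 1 asks. No section says how to score it.

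This matters because the short stay is the barrier that the study sets out to test. The Study Rationale says that infants usually go home 3 to 7 days after cooling and that this limits the time for neurodevelopmental assessment. Assessment 1 includes the TIMP, the GMA and six parent questionnaires, so it is a plausible item to slip past discharge. If late assessments count as successes, the barrier disappears from the result. If the rule is settled only after the data are seen, there are two possible answers to a primary aim and a free choice between them.

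**Working it through.** The plan gives no figure to reproduce. Section 9.2 states that there is no power analysis, and H1 has a threshold but no null rate. The check is a comparison of texts followed by a simple count.

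**Step 1. Which H1 items may fall after discharge?**

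| H1 item | Where or when the plan puts it | Explicit post-discharge allowance? |
|---|---|---|
| Baseline survey | CHLA NICCU, before intervention (6.2.2) | No |
| Two SMI sessions | CHLA NICCU (5.1, 6.1) | No; omitted for referred infants |
| Assessment 1 | Before discharge or in the week after it (6.2.3) | Yes |

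The mismatch is confined to the assessment.

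**Step 2. How far can the two readings differ?** Let E be the number of eligible infants, C the number who enroll and complete all items under the 6.2.3 window, and L the number among those C whose Assessment 1 came after discharge.

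- H1 as worded: C / E
- H1 for the question asked: (C − L) / E
- The result changes from met to not met when L > C − 0.8E

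Section 1.1 and the Précis supply the 80% threshold and the 20 dyads. E, C and L are not in the documents and are assumed. Take E = 20, all 20 enrolled, none referred, and C = 18. H1 as worded is then 18/20 = 90%, and the change point is L > 18 − 16 = 2.

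| Late assessments (L) | Completed before discharge | 80% reached? |
|---|---|---|
| 0 | 18/20 = 90% | Yes |
| 2 | 16/20 = 80% | Yes |
| 3 | 15/20 = 75% | No |
| 9 | 9/20 = 45% | No |
| 18 | 0/20 = 0% | No |

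The last row is the logical limit: H1 as worded would still read 90%.

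**Step 3. Sensitivity to the assumed counts.** With E = 20 and C = 16, one late assessment is enough: 16/20 = 80% becomes 15/20 = 75%. If some eligible families decline, the denominator exceeds 20. With E = 22 and C = 18, H1 is 18/22 = 81.8%, and one late assessment gives 17/22 = 77.3%.

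**Step 4. Would date scoring alone be enough?** No. Referred infants omit the two NICCU sessions by design. If they stayed in the denominator and only NICCU sessions counted, 5 referred infants among 20 (assumed) would cap H1 at 15/20 = 75%, whatever the NICCU team achieved. The rule has to say where these infants belong.

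**The case against.** The strongest reply is that H1 should not be read apart from the question directly above it, which contains the discharge limit. On that view section 6.2.3 is a collection window and not a scoring rule. Some window is needed in practice, since referred infants are consented within 72 hours of discharge (4.3, 6.2.2). The analysis is descriptive with no test, and forms carry the visit date (7.1), so late assessments could be identified afterwards.

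Much of this stands. The window can stay as it is, and the information will probably exist. But reading the discharge limit into H1 is an inference. No section states it, section 9.1 describes the timing in yet another way, and the promised timing report covers only the sessions. Being able to sort the assessments later does not fix the rule beforehand.

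Two stronger readings are tempting, and the documents do not support them.

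- A reader might infer that the whole of H1 can be met without any evidence from the NICCU. The survey and the two early sessions are placed there, so this holds for the assessment only. H1 does not say which two intervention visits it means, but the schedule makes clear that the two early ones are NICCU sessions.
- A reader might infer from section 9.5 that infants with NE drop out of the Aim 1 analysis, or from section 6.2.1 that they are enrolled without being screened for. Section 9.5 defines no analysis set, H1's denominator is eligible infants in both sections, infants with NE are eligible under criterion 2, and section 4.3 screens for them. Even an HIE-only reading would change the denominator, not when or where the items were done.

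**Conclusion.** The point holds for the assessment component of H1. Aim 1 asks about completion before discharge, H1 sets no such condition, and section 6.2.3 expressly permits Assessment 1 up to a week later. H1 can therefore be declared met without showing that the assessment is feasible in the NICCU.

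Each late assessment lowers the proportion by 1/E, which is 5 percentage points when E = 20. Whether the conclusion changes depends on how many are late, and the documents give no basis for predicting that. The move from 90% to 75% with three late assessments assumes that 20 infants are eligible, all enroll, none is referred and 18 complete everything. It illustrates sensitivity and is not a forecast.

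The HIE/NE and severity wording is a separate editorial inconsistency. It does not cause or enlarge the timing problem. The change is worth making because it settles the answer to a primary aim before the data are read.

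**What to change.** In sections 1.1 and 9.5:

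1. Score H1 by date. An infant counts as a success if the baseline survey, Assessment 1 and both NICCU sessions are all dated on or before NICCU discharge. The denominator is eligible infants cared for in the CHLA NICCU, including those whose families decline.
2. Report Assessment 1 completed within 7 days after discharge as a separate, secondary proportion. The collection window in section 6.2.3 need not change.
3. Report referred infants separately and outside the H1 denominator.

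As wording corrections only, make sections 6.2.1 and 9.5 refer to HIE or NE, in line with 1.1 and 4.3, and reconcile the severity wording of Aim 1 with inclusion criterion 2.

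The cost is a text amendment. Visit dates are on the study forms and visit records go into REDCap (7.1), the NICCU discharge summary is obtained (6.2.2), and the screening log records eligible infants who do not take part (4.3). The downside is that H1 may look less favourable, and its denominator will be smaller if referred infants would otherwise have been counted.
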